#### Plans for sampling, recruiting and retaining subjects:

- Sample type: Convenience sample
- Sampling procedures: Convenience sampling will be used to enroll a cohort of breast cancer patients with dyslipidemia (low and medium risk of ASCVD), and randomly separate them into two groups. We prepare to use SPSS software to do the randomly separation. Experimental group used statins, the other one used dietary intervention instead of statins.
- Recruitment method: When patients presented our hospital diagnosed of breast cancer with dyslipidemia (low and medium risk of ASCVD), we will review these patients' medical records to find out the potential subjects for this study according to the inclusion and exclusion criteria. The eligible subject who is willing to participate in this study will be enrolled and consented. They will be randomly (using SPSS software) divided into 2 groups. One is statins group, the other one is control group.

#### Measurements:

- Predictor variables:

The predictor variable we are assessing is whether use statins. According to which, we established the intervention group and control group.

- Outcome variables:

The primary outcome: DFS (disease free survival) rate

Secondary outcome: OS (overall survival) rate

- Potential confounders:

Since this protocol is an RCT (randomly clinical trial) on survival benefits between statins group and control group, it will balance the confoundings in it, such as age, slight pathology difference, tumor size difference, lymph node status difference, tumor grade difference, and the different surgeons between the 2 groups.

- Plans for randomization, blinding, run-in period as needed:

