**Abstract:**

This is a randomized clinical trial from March 28st 2019 to March 28st 2024. The purpose of this study is to evaluate the survival benefits of statins in breast cancer patients with abnormal lipid metabolism. Consecutive samples will be enrolled based on inclusion and exclusion criteria. They will be grouped randomly into intervention group or control group after informed consent. A third group independent from research team will be in charge of randomization. In this study, 348 patients were randomly divided into two groups according to patients' wishes and written informed consent. The experimental group: control group = 1:1. Patients in both groups will undergo breast cancer treatment. The experimental group used statins, while the control group used dietary intervention instead of statins. The main endpoint was 5 years DFS. The subjects were breast cancer patients. For statistical analysis, t-test will be used between two different groups. Estimated sample size will be calculated using t-test. Log rank test was used with survival curve based on Kaplan Merier method and 95% confidence interval of median survival time. Data and Safety Monitoring Board will periodically review, evaluate and give recommendations to this study in various aspects.

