## **Methods:**

### Overview of design:

A randomized, open, blank controlled, single-center clinical trial was conducted to compare the survival benefits of statins in breast cancer patients with dyslipidemia (low and medium risk of ASCVD). The control group used dietary intervention instead of statins. The main endpoint was 5 years DFS. The subjects were breast cancer patients. In this study, 348 patients were randomly divided into two groups according to patients' wishes and written informed consent. The experimental group: control group = 1:1. Subjects were screened and administered continuously until the disease progressed and the toxicity was intolerable. Informed consent was withdrawn or the researcher decided that the drug must be discontinued.

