#### 4) Stratified blocked randomization

In clinical practice, different molecular subtypes do relate to different prognosis and treatment. So we would like to stratify blocked randomization according to molecular subtype. Previous study [12] show that the proportion of luminal A, luminal B, Her-2 positive and triple-negative are 32.73%, 47.01%, 5.71%, 14.55%. And we will do subgroup analysis.

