Appendix

Statins VS. Dietary Intervention on Breast Cancer Patients

Date: --/-- [dd / mm / yyyy]

Name: \_\_\_\_\_

Address: \_\_\_\_\_

ID No.: \_\_\_\_\_

Medical record No.: \_\_\_\_\_

Sex: Female

Date of birth: --/-- [dd / mm / yyyy]

Pathology: \_\_\_\_\_ molecular type \_\_\_\_\_

T \_\_\_\_\_ N \_\_\_\_\_ M \_\_\_\_\_

ER \_\_\_\_\_ PR \_\_\_\_\_ Her-2 \_\_\_\_\_

Ki-67 \_\_\_\_\_ P53 \_\_\_\_\_

Date of surgery \_\_\_\_\_ surgery type \_\_\_\_\_

Other treatment \_\_\_\_\_

Baseline: date \_\_\_\_\_ statin \_\_\_\_\_

LDL-C \_\_\_\_\_ TC \_\_\_\_\_ TG \_\_\_\_\_ ALT \_\_\_\_\_ CK \_\_\_\_\_ Fatty Liver \_\_\_\_\_

1 month follow-up: date \_\_\_\_\_ statin \_\_\_\_\_

LDL-C \_\_\_\_\_ TC \_\_\_\_\_ TG \_\_\_\_\_ ALT \_\_\_\_\_ CK \_\_\_\_\_ Fatty Liver \_\_\_\_\_

3 month follow-up: date \_\_\_\_\_ statin \_\_\_\_\_

LDL-C \_\_\_\_\_ TC \_\_\_\_\_ TG \_\_\_\_\_ ALT \_\_\_\_\_ CK \_\_\_\_\_ Fatty Liver \_\_\_\_\_

6 month follow-up: date \_\_\_\_\_ statin \_\_\_\_\_

LDL-C \_\_\_\_\_ TC \_\_\_\_\_ TG \_\_\_\_\_ ALT \_\_\_\_\_ CK \_\_\_\_\_ Fatty Liver \_\_\_\_\_

RT (recurrence time)\_\_\_\_\_

Other event\_\_\_\_\_

1 year follow-up: date\_\_\_\_\_statin\_\_\_\_\_

LDL-C\_\_\_\_\_TC\_\_\_\_\_TG\_\_\_\_\_ALT\_\_\_\_\_CK\_\_\_\_\_Fatty Liver\_\_\_\_\_

RT (recurrence time)\_\_\_\_\_

Other event\_\_\_\_\_

1.5 year follow-up: date\_\_\_\_\_statin\_\_\_\_\_

LDL-C\_\_\_\_\_TC\_\_\_\_\_TG\_\_\_\_\_ALT\_\_\_\_\_CK\_\_\_\_\_Fatty Liver\_\_\_\_\_

RT (recurrence time)\_\_\_\_\_

Other event\_\_\_\_\_

2 year follow-up: date\_\_\_\_\_statin\_\_\_\_\_

LDL-C\_\_\_\_\_TC\_\_\_\_\_TG\_\_\_\_\_ALT\_\_\_\_\_CK\_\_\_\_\_Fatty Liver\_\_\_\_\_

RT (recurrence time)\_\_\_\_\_

Other event\_\_\_\_\_

2.5 year follow-up: date\_\_\_\_\_statin\_\_\_\_\_

LDL-C\_\_\_\_\_TC\_\_\_\_\_TG\_\_\_\_\_ALT\_\_\_\_\_CK\_\_\_\_\_Fatty Liver\_\_\_\_\_

3 year follow-up: date\_\_\_\_\_statin\_\_\_\_\_

LDL-C\_\_\_\_\_TC\_\_\_\_\_TG\_\_\_\_\_ALT\_\_\_\_\_CK\_\_\_\_\_Fatty Liver\_\_\_\_\_

RT (recurrence time)\_\_\_\_\_

Other event\_\_\_\_\_

3.5 year follow-up: date\_\_\_\_\_statin\_\_\_\_\_

LDL-C\_\_\_\_\_TC\_\_\_\_\_TG\_\_\_\_\_ALT\_\_\_\_\_CK\_\_\_\_\_Fatty Liver\_\_\_\_\_

4 year follow-up: date\_\_\_\_\_statin\_\_\_\_\_

LDL-C\_\_\_\_\_TC\_\_\_\_\_TG\_\_\_\_\_ALT\_\_\_\_\_CK\_\_\_\_\_Fatty Liver\_\_\_\_\_

RT (recurrence time)\_\_\_\_\_

Other event\_\_\_\_\_

4.5 year follow-up: date\_\_\_\_\_statin\_\_\_\_\_

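### The plan leaves nodal status, tumour size and age to randomisation and keeps its own stratum out of the primary test: a valid analysis, but one that forgoes available precision and leaves adjustment open to later choice

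*Combined protocol and SAP*

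**What the plan says.** The potential-confounders item under Measurements argues that, because the trial is randomised, "it will balance the confoundings in it, such as age, slight pathology difference, tumor size difference, lymph node status difference". The list continues with "tumor grade difference, and the different surgeons between the 2 groups". No analysis of these factors follows.

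The tests are named only in the Abstract: "For statistical analysis, t-test will be used between two different groups" and "Log rank test was used with survival curve based on Kaplan Merier method". It does not say which of the two is primary. No section names a covariate, a regression model or a stratified test. The Overview of design gives the endpoint: "The main endpoint was 5 years DFS".

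Item 4 of the randomisation plans notes that molecular subtypes differ in prognosis and treatment, and states: "So we would like to stratify blocked randomization according to molecular subtype". The only analysis use it gives to the stratum is "And we will do subgroup analysis".

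The Appendix form has blanks for date of birth, T, N, M, receptor status and Ki-67, and a line reading "Pathology: \_\_\_\_\_ molecular type". It has no separate field for grade.

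**The concern.** Randomisation balances prognostic factors in expectation; any single trial will show some chance difference. The plan lists these factors as possible confounders, and treats subtype as important enough to stratify on, yet gives none of them a part in the primary comparison.

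Two things are at stake. The first is precision: if the factors predict recurrence, an analysis that uses them has more power at the same sample size. Likewise, a test that ignores a prognostic randomisation stratum tends to be slightly conservative. The second is discretion. The trial is open and single-centre. If nodal status turned out unbalanced, the investigators would have to choose between an unadjusted and an adjusted result with outcomes already known, and a reader could not tell what drove the choice.

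**Working it through.** **1. The plan's own sample size.** Statistical issues gives a standardised effect of 0.1, two-sided α of 0.05, power of 0.90, 157 per group and 348 in total. The usual formula gives n = 2 × (1.960 + 1.282)² / 0.1² = 2,102 per group, so 157 is not reproduced. The dropout step does follow: 2 × 157 / 0.9 = 348.9, given as 348. This is a separate problem. Below, 348 / 2 = 174 randomised and 157 evaluable per arm serve only as sample sizes.

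**2. Size of chance imbalance.** For a factor with prevalence p, the SD of the between-arm difference is √(2p(1−p)/174). The documents give no prevalences, so a range is shown.

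| Assumed p | SD (points) | 95% range (points) | Chance of a gap of 10 points or more |
|---|---|---|---|
| 20% | 4.3 | ±8.4 | 2.0% |
| 30% | 4.9 | ±9.6 | 4.2% |
| 40% | 5.25 | ±10.3 | 5.7% |
| 50% | 5.4 | ±10.5 | 6.2% |

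At 40%, the chance of a gap above 5 points is 2 × [1 − Φ(5/5.25)] = 34%. The chance that at least one of three independent factors differs at p < 0.05 is 1 − 0.95³ = 14%.

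**3. Events.** The plan gives a 10-point DFS difference but no control rate. Assuming 5-year DFS of 75% v 85%, events are 157 × 0.25 + 157 × 0.15 = 62.8. For 80% v 90%, they are 157 × 0.20 + 157 × 0.10 = 47.1.

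**4. Power with and without adjustment.** Two simulations used exponential event times and five years of follow-up, with assumed prevalences and prognostic hazard ratios.
- Set A: 314 evaluable patients, three binary factors (prevalence 40%, 40%, 35%), 1,500 runs. The unadjusted test was a Cox test, which is close to the log-rank.
- Set B: 348 patients with 10% dropout, two binary factors (node-positive 40%, larger tumour 50%), 3,000 runs.

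| Set and prognostic HRs | DFS 75% v 85%: unadjusted → adjusted | Gain | DFS 80% v 90%: unadjusted → adjusted | Gain |
|---|---|---|---|---|
| A, none (1, 1, 1) | 59.2 → 59.6% | 0.4 | 70.7 → 70.7% | 0.0 |
| A, moderate (2, 1.5, 1.5) | 61.7 → 63.4% | 1.7 | 69.9 → 71.5% | 1.6 |
| B, moderate (2.5, 1.8) | 61.3 → 64.1% | 2.8 | 71.8 → 73.6% | 1.8 |
| A, strong (3, 2, 2) | 58.3 → 64.3% | 6.0 | 70.3 → 73.4% | 3.1 |
| B, strong (4, 2) | 58.1 → 63.7% | 5.6 | 68.5 → 73.0% | 4.5 |

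The gain runs from about 0 to 6 points, and is 1.6 to 2.8 with moderate factors. Each power near 60% in set A has a simulation standard error of √(0.6 × 0.4 / 1,500) = 1.3 points, so the decimals should not be leaned on. Neither set included subtype strata or age, so the gain for the exact model proposed below was not simulated.

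**5. Type I error.** Under no treatment effect with strong factors (set A), rejection was 3.9% unadjusted and 4.9% adjusted. The simulation standard error is √(0.05 × 0.95 / 1,500) = 0.56 points, so neither shows inflation.

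**6. Can the data carry the model?** Treatment plus three single-parameter covariates is four parameters, or 47.1 / 4 = 11.8 to 62.8 / 4 = 15.7 events each. The smallest stratum, HER2-positive at 5.71%, is 0.0571 × 348 = 19.9 patients. If its event rate matched the overall average (15% or 20% under the two DFS assumptions), it would supply 19.9 × 0.15 = 3.0 to 19.9 × 0.20 = 4.0 events.

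**The case against.** The best defence is that nothing invalid is planned. Read as a statement about expectation, the sentence on balance is correct. The unadjusted log-rank test is valid under randomisation, and its error rate already allows for the chance differences in step 2. One strong prognostic factor, subtype, is controlled by design. All of this stands. A reader might infer that the unadjusted result would be biased, or its false-positive rate inflated, by imbalance; neither reasoning nor step 5 supports that.

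Three further objections also stand.
- The power gain rests on DFS rates, prevalences and prognostic strengths that the documents do not give, and with moderate factors it is small.
- Grade cannot be counted among data already collected. It could at most be recovered from the free pathology entry.
- Adjustment changes the target. In the strong-factor runs of set A at 75% v 85%, the average hazard ratio was 0.570 unadjusted and 0.546 adjusted. It is tempting to call the first figure a diluted error, but marginal and conditional hazard ratios are different quantities. The plan specifies neither.

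What the defence does not answer is that the stratum used to randomise is absent from the primary test, and that nothing fixes in advance whether or how T, N and age would be used.

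**Conclusion.** The point holds as a worthwhile improvement that needs no new data, not as a flaw that invalidates the trial. The plan relies on randomisation for balance, names only unadjusted tests, and does not carry molecular subtype into the primary comparison. It thereby forgoes some precision and leaves adjustment open to choice after results are seen. The loss of precision is certain in direction only if the factors are prognostic; its size depends on the assumptions in step 4. That the investigators would adjust selectively is not stated anywhere; the point is that the plan does not prevent it. Nor should adjustment be read as a remedy for the sample size: a few points of power do not bridge 157 and 2,102 per group.

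**What to change.** Write the following into the analysis plan before outcomes are examined.

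- Primary DFS test: a log-rank test stratified by molecular subtype, comparing arms as randomised.
- Estimate: a Cox model by randomised arm, stratified by subtype and adjusted for nodal status (positive v negative), T stage (one binary split, fixed now) and age (continuous). Report the hazard ratio with its 95% confidence interval and state that it is conditional on these covariates.
- Marginal summary: Kaplan-Meier 5-year DFS rates by arm.
- OS: use the same model only if the number of OS events allows.
- Grade: leave it out unless a grade field is added to the form.

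The cost is a paragraph of text and slightly more analysis; every item needed is on the Appendix form. There are two small downsides: the hazard ratio is conditional rather than marginal, and the HER2-positive stratum will contribute few events. The sample-size calculation needs its own correction.

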#### 1) Randomization

We prepare to use SPSS software to do the randomly separation. According to the inclusions and exclusions, once we find the right patient, we will put the name in computer. The computer will randomly tell which group the patient will be in. After explanations to the patients, and receiving the patient agreements, we will sign the informed consent with them.

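### The plan gives no single allocation procedure: the abstract puts an independent group in charge, while the operating text has the recruiting team obtain the arm, with no stated concealment or link to the stratified blocks

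*Combined protocol and SAP*

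**What the plan says.** Four places in the combined protocol and SAP bear on how a patient receives an arm.

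- **Abstract.** "A third group independent from research team will be in charge of randomization". The ratio is stated as "The experimental group: control group = 1:1".
- **Plans for sampling, recruiting and retaining subjects.** After describing how the team reviews records and enrols willing patients, the text says "They will be randomly (using SPSS software) divided into 2 groups".
- **1) Randomization.** "We prepare to use SPSS software to do the randomly separation". Then "once we find the right patient, we will put the name in computer", and "The computer will randomly tell which group the patient will be in". The same first-person plural then signs consent with the patient.
- **4) Stratified blocked randomization.** "So we would like to stratify blocked randomization according to molecular subtype". The expected shares of "luminal A, luminal B, Her-2 positive and triple-negative are 32.73%, 47.01%, 5.71%, 14.55" percent are given, and a subgroup analysis is promised. No block size is given.

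The Overview of design describes the trial as open and single-centre. The list of potential confounders under Measurements relies on randomization to balance age, tumour size, nodal status, grade and other factors.

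**The concern.** The sections disagree on who performs allocation. The abstract removes it from the research team, and the operating text gives the visible steps to the people who find and consent patients. The operating text also mentions none of what stratified blocks need: a stratum entered before the arm is released, a prepared list, someone to hold it, and a means of keeping the next assignment hidden.

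This matters because treatment is open. Section 2) Blinding covers only the intention behind the grouping, so it does not make up for weak allocation. Concealment is the main defence against recruiters choosing whom to enrol, or when, in the light of the coming arm. If it fails, the DFS comparison is open to selection bias that analysis cannot reliably remove. Separately, if the blocks are not applied, the planned balance on molecular subtype is left to chance, and the smallest subgroups would suffer most.

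**Working it through.** The plan states no figure to reproduce. The check is a comparison of the text, followed by arithmetic on what is lost if the blocks are not applied or are not concealed.

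**Step 1. Comparison of the sections**

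| Question | Abstract | Sampling plan and 1) Randomization | 4) Stratified blocked randomization |
|---|---|---|---|
| Who is in charge? | Independent third group | The team, using SPSS | Not stated |
| What is entered? | Not stated | Patient's name | Not stated |
| Stratified or blocked? | Not stated | Not stated | Yes, by subtype; size not given |
| Who holds the list? | Not stated | Not stated | Not stated |
| Concealed from recruiters? | Not stated | Not stated | Not stated |

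The first row conflicts. The others show that the described step and the stratified design are not connected.

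**Step 2. If the described step is followed literally (simple 1:1 randomization)**

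Inputs: N = 348 (Statistical issues), the subtype shares in section 4), and allocation probability 0.5.

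- Size of one arm: SD = √(348 × 0.5 × 0.5) = √87 = 9.33. The central 95% range is 174 ± 1.96 × 9.33, which is 156 to 192.
- Expected strata: luminal A 348 × 0.3273 = 113.9, about 114; luminal B 348 × 0.4701 = 163.6, about 164; HER2-positive 348 × 0.0571 = 19.9, about 20; triple-negative 348 × 0.1455 = 50.6, about 51.
- HER2-positive, X ~ Binomial(20, 0.5): a 7:13 or worse split has probability 2 × P(X ≤ 7) = 2 × 137,980 / 1,048,576 = 0.263. For 6:14 or worse it is 2 × 60,460 / 1,048,576 = 0.115.
- Chance of a 60:40 or worse split, by the same exact binomial method: luminal A 3%, luminal B 1%, HER2-positive 50%, triple-negative 16%.

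So the loss of balance falls on the two small strata. The luminal strata, about 80% of patients, would rarely be badly split.

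**Step 3. If recruiters instead held a blocked list with a known fixed block size**

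The plan gives no block size, so sizes 4 and 6 are assumptions. An assignment is fully determined once one arm's places in the block are used up. For a 1:1 block of size 2m, the expected number of determined assignments is 2m/(m + 1), a share of 1/(m + 1).

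- Size 4 (m = 2): 1/3. Enumeration agrees: AABB and BBAA each have 2 determined assignments, and ABAB, ABBA, BABA and BAAB each have 1. That is 8 of 24.
- Size 6 (m = 3): 1/4.

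Steps 2 and 3 are alternatives and should not be added together.

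**The case against.** The strongest defence is that the sections can be read together. The third group may be in charge, with the team merely sending a request, since entering a patient and being told the arm also describes the front end of a list held elsewhere. Section 4) is in the same numbered list as section 1) and may be meant to complete it. SPSS can hold a stratified blocked list, and the registration form in the Appendix has a field for molecular type. Section 3) Run-in design also brings in clinic doctors and an appraiser, so recruiting and allocating roles are not shown to be identical.

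Much of this stands, and it limits what can be claimed. A reader might infer that the team runs allocation on a computer of its own, that the name is the only input, that a draw could be repeated until a preferred arm appears, or that stratified blocks are impossible under this step. The documents support none of these. They do not say whose computer it is or exclude other inputs, and they do not describe whether draws are logged or prepared in advance.

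It is also fair that an uneven split under simple randomization is chance imbalance. It does not bias the DFS comparison or invalidate the log-rank test.

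What the defence does not supply is the procedure. The reconciled reading has to be constructed by the reader. No section says that the team only requests, that the third group holds a list, that subtype is entered, or that upcoming assignments are hidden.

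**Conclusion.** The concern holds as a conflict over who allocates, together with a missing procedure. The abstract and the operating text differ on who carries out allocation, and nothing connects the operating step to the stratified blocks or shows that allocation is concealed in an open, single-centre trial.

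The size depends on what is actually done. Under a literal reading, with 348 patients at the stated subtype shares, the HER2-positive stratum has a 26% chance of a 7:13 or worse split. With a recruiter-held list of known fixed blocks, one third (size 4) or one quarter (size 6) of assignments would be predictable with certainty. The first figure concerns balance. Only the second concerns exposure to selection bias, and it rests on an assumed block size.

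A reader might go further and conclude that neither independent randomization nor stratification exists in this trial, or put a figure on the resulting bias in DFS. The documents do not support either. Both protections are stated, though not carried into the operating step, and there is no information on how many patients might be steered or how their prognosis would differ.

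**What to change.** Replace the allocation sentences in the sampling plan and in section 1) Randomization with one procedure, and refer to it from the Abstract and section 4):

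- The independent third group generates one 1:1 permuted-block list per molecular subtype and holds it. SPSS may be used to generate it.
- Block sizes are withheld from everyone who recruits.
- For a patient whose eligibility and consent are already recorded, the team submits the study number and molecular subtype.
- The third group releases the arm and logs it irrevocably.

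If patients have already been allocated, the sponsor should document the procedure actually used: who held the list, whether subtype was used, and what recruiters could see.

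The cost is protocol wording and a request log. Molecular type is already a field on the registration form. The third group is promised but its capacity is not described, so its ability to answer requests as patients arrive should be confirmed. This change does not settle the wording in the Abstract and Overview of design that ties the random division to patients' wishes, which needs its own correction.

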#### 2) Blinding

The clinicians and patients will be blinded to the intention of the group divided. Since the patients' and clinicians' subjective motion may affect the outcomes.

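### The Randomization section, read in order, allocates the arm before consent, while the Abstract and the recruitment section put consent first

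*Combined protocol and SAP*

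**What the plan says.** Four places bear on the order of consent and allocation.

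- **Randomization (item 1 of the randomization plans).** The trigger is eligibility: "once we find the right patient, we will put the name in computer". The text continues: "The computer will randomly tell which group the patient will be in. After explanations to the patients, and receiving the patient agreements". Signing of consent is the last step described.
- **Abstract.** "They will be grouped randomly into intervention group or control group after informed consent". It adds: "A third group independent from research team will be in charge of randomization".
- **Plans for sampling, recruiting and retaining subjects.** "The eligible subject who is willing to participate in this study will be enrolled and consented. They will be randomly (using SPSS software) divided". The tool is named as the team's own: "We prepare to use SPSS software to do the randomly separation".
- **Run-in design (item 3).** Consent and a registration form follow directly once a patient is found eligible. Allocation is not mentioned.

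Three further statements matter. The Overview of design calls the trial open. The Blinding item says only: "The clinicians and patients will be blinded to the intention of the group divided". Under Potential confounders, the plan relies on randomization for comparability ("it will balance the confoundings in it"), naming age, pathology, tumour size, nodal status, grade and surgeon.

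**The concern.** The section that describes how randomization is run appears to place allocation before consent, and two other sections place it after. The order decides whether anyone involved in enrolment can know the arm while the patient's participation is still undecided.

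The arms are visibly different: a statin against dietary intervention. A recruiter who already knows the arm may be more or less ready to approach a given patient, or may explain the trial differently. A patient who is told her arm may be more or less ready to agree. If any of this relates to prognosis, the enrolled groups differ at baseline for reasons that randomization did not create. Stratifying by molecular subtype does not protect age, tumour size, nodes or grade within a subtype, and the plan specifies no adjusted analysis that might partly correct for them.

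**Working it through.** **1. Order of steps, section by section**

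| Section | Order as written |
|---|---|
| Randomization | eligible → name entered → arm stated → explanation and agreement → consent signed |
| Abstract | consent → randomized |
| Sampling and recruitment | willing and eligible → enrolled and consented → randomized |
| Run-in design | eligible → consent and registration form (allocation not mentioned) |

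The Abstract and the recruitment section agree with each other, and the run-in text is compatible with them. The Randomization section differs.

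**2. Is the arm protected before consent by any other text?**

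- *Independent group.* The Abstract's third group could keep the upcoming sequence hidden. The recruitment and Randomization sections do not mention it, and the latter uses the same first-person plural for finding the patient, entering her name and signing consent. Even an independent group gives no protection if it releases the arm before consent.
- *Blinding.* That item covers the intention behind the grouping. It does not say that the arm is withheld, and the design is open.
- *Stratified blocks.* Item 4 governs how the list is built, not when an assignment is released.

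So nothing prevents recruiters from seeing the arm early. That they would see it is an inference, because the Randomization section does not say who views the computer's output.

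**3. Scale (illustration, not an estimate)**

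The plan gives no figure that depends on this order and no refusal rates, so the bias cannot be computed. The following shows only how sensitive the comparison is.

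Inputs:
- n = 157 per arm, from Statistical issues, Primary outcomes, taken as given.
- p = 5-year DFS with no true effect: 0.70, 0.80 or 0.90 (assumed).
- b = shift in one arm's DFS caused by selection (assumed).

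Formulas:
- SE = √{[(p+b)(1−p−b) + p(1−p)] / 157}
- False-positive risk = P(|Z + b/SE| > 1.96)

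Example with p = 0.80 and b = 0.04:
- SE = √[(0.84×0.16 + 0.80×0.20)/157] = √(0.2944/157) = 0.0433
- b/SE = 0.924
- Risk = P(Z > 1.036) + P(Z < −2.884) = 0.150 + 0.002 = 0.152

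| b (points) | p = 0.70 | p = 0.80 | p = 0.90 |
|---|---|---|---|
| +2 | 0.068 | 0.074 | 0.095 |
| +4 | 0.124 | 0.152 | 0.258 |
| +6 | 0.224 | 0.295 | 0.555 |
| −4 | 0.118 | 0.137 | 0.194 |

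An exact binomial calculation with the pooled two-proportion test gives 0.124, 0.151 and 0.253 at +4 points. A log-rank simulation (exponential times, complete 5-year follow-up, 4000 runs) gives 0.126, 0.154 and 0.251. The result does not hinge on the normal approximation.

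**The case against.** The strongest reply is that the conflict rests on sentence order alone. The Randomization section has no connecting word between the computer's output and the approach to the patient, and its one temporal word governs only the signing of consent. It could be read as two separate statements, one on how the arm is generated and one on how consent is obtained. The English is loose throughout, the Abstract is explicit that consent comes first, and no text ranks the Randomization section above the others. Harm also needs a chain of events: the section is followed literally, recruiters see the arm, approach or refusal depends on it, and that dependence relates to prognosis. Finally, the error rates rest on assumed inputs, and the log-rank check assumes complete 5-year follow-up although the Abstract dates the whole trial from March 2019 to March 2024.

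Much of this is fair. The conflict does rest on sentence order, the chain is conditional, and the figures show sensitivity only. But the section reads as a procedure: it starts from a trigger, that trigger is eligibility, and nothing in it places consent before the name is entered. If the Abstract's order is intended, the section describing the procedure still misstates it and needs the same correction. The objection also leaves the main gap open, because no section withholds the arm from recruiters until consent.

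Two related points are unclear rather than contradictory. A third group could be the one operating SPSS, so who allocates is merely unstated. The phrase in the Abstract and the Overview of design about dividing patients according to their wishes can mean willingness to take part; no section has a patient choosing her arm.

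**Conclusion.** The concern holds. As written, the Randomization section puts allocation before consent, against the Abstract and the recruitment section, and nothing in the plan conceals the arm from recruiters in an open trial. This must be fixed, because selection at entry cannot be undone afterwards and the plan depends on randomization for balance.

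The size is unknown. The bias is zero if approach and refusal do not depend on the arm, and this route is closed if consent comes first and the independent group holds the assignments. Under the assumed inputs, a 2-point selection bias moves the false-positive risk from 5% to between 6.8% and 9.5%, and a 6-point bias moves it to between 22% and 55%. Only the 157 per arm comes from the plan; the DFS levels and the biases are assumptions.

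**What to change.** - Rewrite the Randomization section in one order: eligibility confirmed; written consent signed; patient registered; arm then released by the Abstract's independent group from the list stratified by molecular subtype. State that recruiters have no access to the arm before registration.
- Identify that group in the Randomization and recruitment sections, and say who operates SPSS and who holds the list.
- In the Abstract and the Overview of design, replace the wording about patients' wishes with a plain statement that allocation follows written informed consent.

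The cost is protocol wording and a small operational step: the independent group must hold the list and release each assignment after registration. No patients or visits are added.
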